#### **Endpoints**

Day 1 post intervention – GCF/plaque/blood samples, blood pressure

Day 7 post intervention – GCF/plaque/blood samples, blood pressure

Day 90 post intervention – Full mouth pocket and bleeding scores & periodontal charting, blood pressure, BMI and sample collection (GCF/plaque/blood)

#### **Primary Outcome:**

Changes in serum CRP. This will be measured:

- Pre-intervention, at baseline visit (as per flowchart)
- Day 1, day 7 and day 90 post-intervention

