## STUDY SYNOPSIS

Title of Study:	The Immune Response after Periodontal Treatment
Study Centre:	Glasgow Dental Hospital
Duration of Study:	36 MONTHS
Primary Objective:	To identify changes in systemic markers of inflammation following periodontal treatment, comparing two standard treatment modalities (hands scaling and ultrasonic scaling)
Secondary Objectives:	To investigate bacteraemia, composition and function of oral bacteria, treatment outcomes following periodontal treatment, patient and operator preferences, and treatment time comparing hand scaling and ultrasonic scaling.
Primary Endpoint:	C-reactive protein in the circulation following treatment.
Rationale:	To determine whether hand scaling or ultrasonic scaling are different at inducing a systemic inflammatory response.
Methodology :	RCT
Sample Size:	42 patients (TBC)
Screening:	Patients referred to Glasgow Dental Hospital Unit of Periodontics requiring periodontal treatment at Glasgow Dental Hospital.
Registration/ Randomisation:	Patients and their samples will be assigned a study code. There will be (stratified) randomisation to treatment with either hand scaling or ultrasonic scaling
Main Inclusion Criteria:	
 
• Provision of signed, written, informed consent to participate
 
• Men or women aged 18 years to 70 years inclusive
 
• Periodontal disease requiring treatment at Glasgow Dental Hospital
 

Main Exclusion Criteria:	
 
• Known or suspected high risk for tuberculosis, hepatitis B or HIV infections
 
• Require interpreter/non English language written material to understand and provide, or any other reason for being unable to provide written, informed consent
 
• History of bleeding diathesis
 
• Females using contraceptive methods.
 
• Pregnant or lactating females.
 
• Reported diagnosis of any systemic illnesses including cardiovascular, renal, and liver diseases.
 

	
 
• Any pharmacological treatment within 3 months before the beginning of periodontal treatment.
 
• Specialist Periodontal treatment in the previous 6 months.
 
• Patients who will not tolerate Ultrasonic instrumentation even with local anaesthesia.
 

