## SCHEDULE OF ASSESSMENTS

Study Procedure	Screening initial consultant appointment	Base line	TREATMENT VISITS	DAY 1 WITHIN 24HR	Day 7 +/- 24HR	Day 90 +/- 10DAY
Study information given	Y					
Review Inclusion/Exclusion Criteria	Y	Y	Y	Y	Y	Y
Obtain initial indication if patient will consider study and appoint for combined study/first treatment visit	Y					
Obtain written consent		Y				
Randomisation		Y				
FMPS & FMBS & Periodontal charting	*	Y				
Blood Collection ( 8-10am )		y				
blood pressure and BMI record		y				
Medical History	Y	Y	Y	Y	Y	Y
OHI		y	Y		Y	Y
Sample collection (blood, plaque, GCF, saliva)		√		Y	Y	Y
Obtain^/Review consent			Y	Y	Y	Y
Complete CRF		Y	Y	Y	Y	Y

\*deepest site on each tooth recorded only

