## 4.2 Study Outcome Measures

### 4.2.1 Primary Outcome Measure

*Changes in serum CRP pre compared with post treatment.*

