#### ***Blinding***

Both the patients and clinicians will remain blinded to the intervention until the intervention is carried out. Research personnel will remain blinded to specific patient allocation throughout the process through the means of patient barcodes. The key linking the barcodes to the patients will be available to the Chief Investigator. The intervention codes will only be available once the key analyses have taken place.

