#### ***Sample Size***

The sample size calculation is based on data from previous published studies that measured changes in CRP following periodontal treatment. From these studies a difference of 3.5 mg/l (SD=3 mg/l) in CRP was detected between the two groups receiving different schedules of periodontal treatment (quadrant vs full mouth debridement) at primary endpoint. Therefore at 80% power and a 5% significance level, a sample size of n=34 (17 in each group) is required to detect a minimum difference of at least 1 standard deviation (3 mg/l) between the change in CRP levels from baseline to primary endpoint between the two groups (hand vs ultrasonic). To account for potential drop out of 20% we aim to recruit 42 eligible patients to the study.

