#### **General Principals**

Data will be summarised for patients in both groups. Categorical variables will be summarised with the number of observations and missing values, and number and percentages of patients falling into each category. Continuous variables will be summarised using the number of observations and number missing, mean, standard deviation (SD), median, 25th and 75th quartiles (Q1 and Q3 respectively), minimum and maximum values. Formal comparisons will be made between the treatment groups using appropriate tests depending on the nature of the data, this may include Chi-Squared tests, Fisher Exact Tests, two sample t-tests and Mann Whitney tests.

Analysis: the effect of treatment group (Manual vs ultrasonic) on changes in CRP levels (and other secondary outcomes):

- Appropriate generalised linear models
- Binary logistic models (for dichotomous outcomes)

Models may be adjusted for age, gender, deprivation levels, operator, smoking, baseline disease levels.

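### The trial is sized for one 5% comparison of CRP change, but the plan never says whether the deciding visit is Day 1, Day 7 or Day 90

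*Combined protocol and SAP*

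**What the plan says.** The Sample Size text in section 5.1 requires 17 patients per group to detect 3 mg/l, stated as one SD, "between the change in CRP levels from baseline to primary endpoint between the two groups (hand vs ultrasonic"). It uses primary endpoint in the singular and attaches no day to it.

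The other places where a day could have been given do not give one:

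- **Synopsis, Primary Endpoint:** "C-reactive protein in the circulation following treatment".
- **Section 4.2.1:** "Changes in serum CRP pre compared with post treatment".
- **SAP, Endpoints:** three visits in sequence, starting with "Day 1 post intervention – GCF/plaque/blood samples, blood pressure" and followed by Day 7 and Day 90. None is marked as primary.
- **SAP, Primary Outcome:** serum CRP at baseline and then "Day 1, day 7 and day 90 post-intervention", again unranked.
- **SAP, General Principals:** plans an analysis of "the effect of treatment group (Manual vs ultrasonic) on changes in CRP levels", using generalised linear models or tests to be chosen according to the data. It states no primary visit, repeated-measures structure or multiplicity rule.
- **Section 5.2 (Primary efficacy analysis):** says that no efficacy analysis applies.

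On masking, the Blinding text says: "The intervention codes will only be available once the key analyses have taken place". It does not define the key analyses.

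**The concern.** The three visits answer different questions. The background and rationale (sections 1.1 and 1.2) concern the response straight after instrumentation, whereas Day 90 is the review visit with full charting. A difference at Day 1 and a difference at Day 90 would support different conclusions, yet under the present text either could be reported as the primary result.

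The sample size assumes one test at 5%. With three unranked candidate contrasts and no rule for combining them, the deciding contrast could be selected after the results are known, and the stated error rate would then not apply. Withholding the intervention codes hides which arm is which. It does not prevent two coded groups from being compared at all three visits, so it limits the choice without removing it.

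**Working it through.** **1. Reproduce the planned sample size.** Inputs from the Sample Size text: difference 3 mg/l, SD 3 mg/l, power 80%, significance level 5%, equal groups. Sidedness is not stated; two-sided is assumed.

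- Normal approximation: n per group = 2 × (1.960 + 0.842)² × 3² / 3² = 15.7, rounded up to 16.
- Two-sample t-test: the solution is 16.71, rounded up to 17 per group, or 34 in total. This matches the plan. Power at 17 per group is 80.7%.
- One-sided (normal approximation): 13 per group, which does not match, so the two-sided reading is the right one.
- Dropout of 20%: 34 / 0.8 = 42.5, so 43; or 17 × 1.2 = 20.4, so 21 per group and 42 in total, as stated.

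The arithmetic is sound, and it is for **one** test.

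**2. Error rate if three visits are each tested.** Assumed rule: a two-sample t-test of CRP change at each visit at two-sided 5%, with success if any one is significant.

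For independent tests: 1 − 0.95³ = 1 − 0.857375 = 14.3%.

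For correlated tests, 200,000 trials with no treatment effect were simulated per scenario, with three change scores per patient and equal between-visit correlation. The documents give no correlations, so the range is an assumption.

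| Between-visit correlation | 17 per arm | 21 per arm |
|---|---|---|
| 0 | 14.3% | 14.1% |
| 0.3 | 13.6% | 13.8% |
| 0.5 | 12.8% | 12.5% |
| 0.7 | 10.9% | 11.1% |
| 0.9 | 8.5% | 8.5% |

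The single-test rate with 17 per arm was 4.9% to 5.1%.

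**3. Skewed data.** With log-normal change scores (log-SD 1) and 17 per arm, the rates were 10.9%, 10.1% and 7.0% at underlying correlations 0, 0.5 and 0.9. One test gave 3.8%.

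Ratios to the single-test rate:

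- Normal: 8.5 / 5.0 = 1.7 to 14.3 / 5.0 = 2.9.
- Log-normal: 7.0 / 3.8 = 1.8 to 10.9 / 3.8 = 2.9.

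**4. Shared baseline.** All three changes subtract the same baseline value. If the four CRP values have equal variance σ² and equal correlation ρ, each change has variance 2σ²(1 − ρ) and each pair has covariance σ²(1 − ρ). The change scores then correlate at exactly 0.5, whatever ρ is. A cross-check of 40,000 trials simulated baseline plus three later values:

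- Normal: 11.2% to 12.7%.
- Normal, Day 1 SD three times the others: 13.4% to 13.9%.
- Log-normal: 8.8% to 10.5%, against 3.5% to 4.3% for one test.

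**5. Cost of keeping three co-equal primary tests.** With a Bonferroni level of 0.05 / 3 = 0.0167, the t-test solution is 22.4, so 23 per group or 46 evaluable, and 46 / 0.8 = 57.5, so 58 recruited. At 17 per group, power at each visit would be about 65%.

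**The case against.** The strongest reply is that an early visit was plainly meant. Sections 1.1 and 1.2 speak of an immediate response, the Sample Size text uses a singular endpoint, and it draws on a comparison of quadrant with full-mouth debridement, which fits the acute-phase trial in the reference list. The flow chart and the diagram announced in section 1.2 are not shown in the copy reviewed, and either might mark the visit. These hints are fair, but none defines the endpoint. The SAP refers to the flow chart only for the baseline visit, and even if a figure named a day, the outcome, sample size and SAP text would still need to state it.

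A second objection is that the inflation figures rest on a testing rule that the plan does not contain. One model with a single treatment effect would also fit the SAP and would carry no inflation. That stands: the figures show what the text permits, not what it prescribes. It also stands that the shared-baseline results, about 9% to 14%, are more realistic than the extremes of the wider range.

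Third, section 3.3 masks the researcher doing the analysis, and the codes are held back. This protects against choosing a visit because it favours a known arm. It does not stop someone choosing the visit at which the coded groups differ.

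Finally, this is a 42-patient comparison of two standard treatments, so the priority given to the point is a matter of judgement. The gap nevertheless concerns the trial's one confirmatory contrast and cannot be credibly closed after comparisons have been seen.

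**Conclusion.** The concern holds and must be fixed. The sample size calculation is correct for one two-sided 5% test, but no readable part of the plan says at which visit that test is made, and nothing ranks or combines the three visits.

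If any significant visit counted as success, the false-positive rate would be about 1.7 to 2.9 times the single-test rate: 8.5% to 14.3% with normal change scores and 7.0% to 10.9% with log-normal ones. This depends on that unstated rule and on assumed correlations and distributions. The absence of a named visit depends on neither, and confidence in it is high, subject to the figures that are not shown.

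**What to change.** Before any CRP comparison between groups, coded or not, and before the intervention codes are released, put one definition in the synopsis, section 4.2.1, the Sample Size text and the SAP Primary Outcome. For example:

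> The primary outcome is change in serum CRP from baseline to [named visit], compared between arms with one two-sided 5% test; CRP changes at the other two visits are secondary.

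- **Choice of visit.** This is the team's. Day 1 is one example that fits the rationale in section 1.2. If it is chosen, the Schedule of Assessments ("DAY 1 WITHIN 24HR") and section 4.1 (24 ± 18 hours, so 24 − 18 = 6 to 24 + 18 = 42 hours) must be reconciled.
- **Consistency.** Mark the primary visit in the SAP Endpoints list, and bring section 5.2 into line so that it does not deny the analysis just defined.
- **Source of the SD.** State at which time the 3.5 mg/l difference (SD 3 mg/l) was observed, and whether that SD applies to change at the named visit. If it does, 17 per arm is unchanged. If not, restate the power.
- **Alternative.** If all three visits are to be primary, specify one joint test across visits or a fixed testing order, and recheck the power for the rule chosen.

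The cost is wording in the four places, the two consistency edits, a check of the source data and, if Day 1 is chosen, the window reconciliation. No extra patients, visits or samples are needed if the SD of 3 mg/l applies at the named visit. The price is that a CRP difference at another visit can no longer be claimed as the primary finding.

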#### **Secondary Outcomes:**

Microbiome (continuous and discrete data)

- Microbiome analysis of plaque
- Species diversity
- Collected pre intervention (at baseline visit)
- Collected post intervention (at day 1)

Bacteraemia analysis (continuous data)

- Collected simultaneously with serum CRP
  - Day 1, day 7 and day 90 post intervention

Inflammation and immune analysis (continuous data)

- GCF – cytokine measurements
- Serum cytokine measurement
- Serum antibody (anti-bacterial/auto antibody)
- Collected simultaneously with serum CRP
  - Day 1, day 7 and day 90 post intervention

Clinical outcomes (discrete data)

- Periodontal Probing Depths (at day 90 post intervention)
- Loss of attachment (at day 90 post intervention)
- Plaque/gingival indexes
- Blood Pressure
- Treatment time (time spent on debridement)

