
Statistical Analysis:
	
Different types of data will be generated from the study, e.g.
 
 
- Serum CRP pre and post treatment.
 
- Serum cytokine levels pre and post treatment
 
- Bacteraemia pre and post treatment
 
- Composition and function of oral bacteria pre and post treatment.
 
- Clinical data to provide a measure of severity and extent of periodontal disease pre and post treatment.
 
- Patient centred outcomes of each treatment modality.
 
- See statistical analysis plan (SAP) for further details.
 

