#### **Baseline visit:**

If the patients initially said YES to participating in the study at the screening visit, at this visit, prior to the start of treatment the patient will be asked if they have further considered participation in the study. If yes, consent for sample collection will be sought and samples will be collected by the GDHCRF research nurse and/or dentist/hygienist (the hygienist or dentist will generally only collect plaque samples as s/he will be removing the plaque anyway). This visit includes FMPS & FMBS & Periodontal charting, blood pressure recording, BMI recording and sample collection of GCF, plaque & blood). This visit is also for initial periodontal charting and initial treatment. This visit includes detailed tooth and gum home care instructions and a superficial scaling of the teeth. This is usually carried out by a staff or research hygienist, but may also be undertaken by training grade staff under the supervision of a consultant.

gingival indices will be taken. The patient will then be randomised to full mouth non-surgical periodontal treatment using either hand scalers or ultrasonic instrumentation. Appointments will be made for patient to attend for treatment visits, Day1, Day 7 and Day 90 visits with time in the GDHCRF for sample collection / blood pressure, BMI and periodontal charting where applicable.

**Treatment visits** - full mouth non-surgical periodontal treatment will be carried out within a 24hr period (+/- 18hr) either using hand instrumentation or ultrasonic instrumentation as per randomization. At the last treatment visit the clinician will verbally enquire whether the patient is happy to continue participation in the study. If yes - then the patient should attend Day 1 (24hrs later (+/- 18hrs) with time in the GDHCRF for sample collection / blood pressure recording.

**Day 1** - 24 hours (+/-18hrs) after treatment completed, further samples (GCF/Plaque/blood) and blood pressure recording will be performed. At this visit the clinician will verbally enquire whether the patient is happy to continue participation in the study. If yes - then the patient should attend Day 7 (+/- 1 day) with time in the GDHCRF for sample collection / blood pressure recording, & review of ohi

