**Day 7** – 7 days after treatment completed, further samples (GCF/Plaque/blood) and tests (blood pressure recording and medical history update) will be performed. At the last treatment visit the hygienist will verbally enquire whether the patient is happy to continue participation in the study. If yes - then the patient should attend the Day 90 visit (+/- 10days) with time in the GDHCRF for sample collection / blood pressure recording, plaque index & review of oral hygiene.

**Day 90** - 90 days after treatment (+/- 10 days) Patient appointed jointly to the GDHCRF and for review with consultant or training grade staff / hygienist under consultant supervision. FMPS & FMBS & periodontal charting, medical history, blood pressure recording, BMI & sample collection of GCF/ Plaque / blood will be taken as at baseline, day 1 and day 7 visits.

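### Baseline is not named as a time point for bacteraemia, cytokines and serum antibody, and adjustment for each marker's own baseline value is not specified

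*Combined protocol and SAP*

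**What the plan says.** Section 4.2.2 and the SAP's Secondary Outcomes list carry the same text. The entries for bacteraemia and for inflammation and immune analysis (GCF cytokines, serum cytokines, serum antibody) each have a parent line, "Collected simultaneously with serum CRP", and beneath it "Day 1, day 7 and day 90 post intervention". Neither entry has a baseline line. In the same lists the microbiome entry has an explicit pre-intervention line, and the SAP's Primary Outcome section gives CRP a pre-intervention measurement as well as the three follow-up days.

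The statistical analysis row of the Synopsis describes the data as "Serum cytokine levels pre and post treatment" and "Bacteraemia pre and post treatment". It mentions neither GCF cytokines nor serum antibody.

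The samples exist. The baseline visit in section 4.1 includes "sample collection of GCF, plaque & blood", the Schedule of Assessments marks sample collection at baseline, and the Day 90 entry says its measurements and samples "will be taken as at baseline, day 1 and day 7 visits".

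The SAP's General Principals section sets the models to estimate the effect of treatment group on changes in CRP and in the other secondary outcomes. Adjustment is optional. The possible covariates include smoking, operator and baseline disease levels, but not the baseline value of the marker being analysed.

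**The concern.** Someone planning the assays from these lists could reasonably reach either of two schedules: four time points (same as CRP) or three (the days written down). Under the second, change in these markers after treatment could not be described, although the Synopsis objective is to identify changes in systemic markers of inflammation, in the plural. A positive Day 1 blood culture or assay could not be told apart from one that was already positive before treatment.

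The model is a separate gap. Even if baseline is assayed, the plan does not say how the value enters the comparison between arms. A change score and a baseline covariate can give quite different precision, and with about 17 patients per arm that difference matters.

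**Working it through.** **1. The time points side by side**

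| Outcome | Baseline named in the outcome list? | Synopsis says pre and post? | Baseline sample collected? |
|---|---|---|---|
| Serum CRP (primary) | Yes | Yes | Yes |
| Plaque microbiome | Yes | Yes | Yes |
| Serum cytokines | No | Yes | Yes |
| Bacteraemia | No | Yes | Yes |
| GCF cytokines | No | Not mentioned | Yes |
| Serum antibody | No | Not mentioned | Yes |

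For all four of the last rows the parent line points to the CRP schedule, which includes baseline, while the line below it lists only follow-up days.

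**2. The plan's own sample size**

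Inputs from the Sample Size section: difference 3 mg/l, SD 3 mg/l (1 SD), 80% power, 5% significance (two-sided assumed; the plan does not say).

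- Normal approximation: n per arm = 2 × (1.960 + 0.842)² ÷ 1² = 15.7, so 16.
- Two-sample t-test: 16.7, so 17 per arm, with power 80.7% at 17.
- Drop-out: 34 ÷ 0.8 = 42.5, against 42 stated.

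The plan's 17 per arm reproduces. That calculation is for CRP; no power is claimed for the secondary outcomes.

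**3. What the baseline value is worth for a continuous secondary outcome**

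Assumptions: 17 per arm, 80% power, two-sided 5%, equal SD before and after treatment, correlation r between baseline and follow-up. The documents give no r, so a range is used. SD means the SD of a single follow-up value.

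Variance of the arm comparison relative to follow-up values alone:

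- follow-up value alone: 1
- follow-up value with baseline as covariate: 1 − r²
- change score: 2(1 − r)

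The two-sample t-test at 17 per arm gives a detectable difference of 0.991 SD for follow-up values alone. The other methods multiply this by the square root of the relative variance. At r = 0.5, for example, the covariate model gives 0.991 × √0.75 = 0.858 and the change score 0.991 × √1.0 = 0.991.

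| r | Relative variance, covariate | Relative variance, change | Detectable, follow-up only | Detectable, covariate | Detectable, change |
|---|---|---|---|---|---|
| 0.3 | 0.91 | 1.40 | 0.991 | 0.945 | 1.173 |
| 0.5 | 0.75 | 1.00 | 0.991 | 0.858 | 0.991 |
| 0.7 | 0.51 | 0.60 | 0.991 | 0.708 | 0.768 |

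Power for an assumed true difference of 0.8 SD is 62% for follow-up values alone. With the covariate it is 66%, 74% and 89% at the three correlations. With a change score it is 48%, 62% and 83%.

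The calculation ignores the one degree of freedom spent on the covariate. It applies to continuous outcomes and does not carry over to bacteraemia analysed as positive or negative.

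**The case against.** The strongest reply is that the plan already implies baseline. The parent line refers to CRP, CRP is measured at baseline, the samples are taken, and the SAP intends to analyse changes. These lists also tend to name follow-up times without excluding baseline: the SAP's Endpoints section gives only Days 1, 7 and 90 for blood, which includes the CRP sample, and probing depths are listed at Day 90 only although charting is done at baseline. This stands. It rules out several stronger readings that a reader might infer:

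- *That baseline was left out on purpose.* Nothing in the documents shows intent, and the Endpoints and probing-depth entries point to loose wording.
- *That change or baseline-adjusted comparisons are lost.* The samples exist and analysis of change is planned.
- *That the Synopsis contradicts the lists for all four outcomes.* It does so for serum cytokines and bacteraemia only. For GCF cytokines and serum antibody the inconsistency is with the parent line and with the planned analysis of changes.
- *That a comparison of follow-up values would be biased.* In a randomised trial chance baseline imbalance is covered by the standard error. The cost is precision.

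It can also be said that the figures price an analysis of follow-up values alone, which the documents do not plan. That is fair, and it is why the change score is shown as well. The reply does not settle two things: which schedule an assay plan should follow, and how the marker's own baseline value enters the model.

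**Conclusion.** The point holds as an inconsistency in the listed time points together with an under-specified model. It concerns secondary outcomes only and does not change the sample size.

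The benefit of the covariate model over follow-up values alone is a variance lower by 9%, 25% or 49% at an assumed correlation of 0.3, 0.5 or 0.7. Assaying baseline does not secure this by itself. If the planned changes are analysed as simple differences, precision is worse than with follow-up values alone below a correlation of 0.5, equal at 0.5 and better above it. The covariate model is at least as precise as either alternative at every correlation in the table. These results rest on equal SDs before and after treatment and on correlations that the documents do not give, so they are a range and not a forecast.

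**What to change.** 1. In section 4.2.2 and in the SAP's Secondary Outcomes list, add baseline (pre-intervention) to the bacteraemia entry and to the inflammation and immune entry, ahead of Days 1, 7 and 90.
2. In the SAP's General Principals section, state that each continuous marker is compared between arms by a model of the follow-up value with that marker's own baseline value as a covariate, in place of a simple change score. For bacteraemia analysed as positive or negative, use baseline status as the covariate.

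The cost is wording in three places, one degree of freedom per model and, where baseline assay was not already intended, one already collected sample per patient for each assay (up to 42 per assay). No extra visit, procedure or patient is needed.
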